11.0 TOXICITIES/SIDE EFFECTS

11.1 IMRT

Potential acute side effects of IMRT are identical to those associated with radiation delivered with conventional 3D techniques. These include mild-moderate erythema, hyperpigmentation, moist desquamation of the chest wall, fatigue, radiation pneumonitis, predisposition for developing a chestwall skin infection, and/or changes in blood count (<3 and will be scored according to the Common Terminology Criteria for Adverse Events (CTCAE) Version 4.0). Additionally, CBC will be measured at specified time points as per standard care. For pre-menopausal women, the first CBC may be consolidated with the pre-study pregnancy test.

Capsular contracture and cosmesis will be graded by the Baker scoring system and Breast-Q[®] questionnaires at time points specified for Group 1 and Group 2.

At any time following completion of radiation, implant failure can be assessed by surgical intervention requiring implant removal or replacement.

Lactating and pregnant women will be excluded because of potential teratogenic effects of radiotherapy that may be harmful to the developing fetus or nursing infant.

11.2 Breast MRI

Side effects of breast MRI include claustrophobia. Gadolinium contrast will be utilized in MRI and in CT simulation, provided the patient is not allergic. Side effects of the injection of Gadolinium include temporary pain, bleeding, and bruising at the injection site. The risk of anaphylactic reaction with gadolinium is small, and a physician will be present for evaluation as per standard care. Patients with tissue expanders or any other ferrous-containing substance within or on the body will not be allowed to undergo MRI due to interaction of the metal port within the expanders with the magnet.

11.3 PET Myocardial Perfusion Scan

Temporary side effects of the vasodilator administration include dyspnea, headache, dizziness, nausea and chest or abdominal discomfort. Rare but serious side effects include fatal arrhythmia and

myocardial infarction. Placement of the angiocatheter for the radiotracer /vasodilator injection may result in temporary pain, bleeding or bruising at the injection site. There is no expected toxicity related to the ¹³N-NH₃ injection.

11.4 Cardiopulmonary Exercise Testing

In appropriately selected patients , graded exercise testing carries a finite risk of adverse cardiovascular event with <1/100,000 in well individuals and 1/10,000 in clinical populations.

11.5 Strain Echocardiogram

Echocardiography is a common test that is performed in patients for cardiac assessment. No radiation is involved with this test and no anticipated side effects are expected.

11.6 Flow-Mediated Dilatation/Ultrasound of the Brachial Artery

The patient will be monitored throughout the testing period for reactions to the prolonged cuff inflation such as arm pain and numbness. These reactions are not unexpected, and should last only seconds. Suprasystolic pressure will be adjusted for patient comfort. There are no expected adverse events from the ultrasound of the brachial artery.

12.0 CRITERIA FOR THERAPEUTIC RESPONSE/OUTCOME ASSESSMENT

For Group 1, at 12 and 24 months (\pm 2 months) and for Group 2, at 18 and 30 months (\pm 2 months) following IMRT, the patient will undergo clinical examination to assess treatment efficacy as well as cosmesis and degree of capsular contracture. The treating radiation oncologist and plastic surgeon will evaluate the patients at these pre-determined time points. However, assessment for the primary endpoint, implant failure, may occur at any time between the end of IMRT to the end of the study follow-up period for each group.

The incidence of capsular contracture and minor revisional surgeries will also be assessed. Breast-Q[®] questionnaires will be used to assess patient-rated cosmesis. Post-treatment MRI studies will be correlated with clinical assessments of capsular contracture to determine the specificity and sensitivity of this diagnostic study as a tool to follow implant patients who were treated with radiation. The quantification of post-radiation changes in the implant and overlying capsule will be descriptive and formulate the basis for future studies.

The rationale for our follow-up period is based on data from our center assessing implant failure rates in patients treated with conventional RT at MSKCC. Given that the bulk of events occurred within the first 2 years after radiation, we believe that 24-30 months of follow-up after radiation is sufficient to capture the proposed endpoints of the study. These data are consistent with other reports in the literature in which approximately 92% of contractures occur within the first 12 months of surgery[50].

13.0 CRITERIA FOR REMOVAL FROM STUDY

If at any time the patient desires to quit participation in the study or is found to be ineligible for the protocol as designated in the section on Criteria for Subject Eligibility (i.e. a change in diagnosis), the patient will be removed from the study.

If at any time the patient develops progressive disease that warrants a change in the radiation treatment plan (planned dose, fractionation, technique, volume), they will be withdrawn from the study and treated with the alternative therapy.

14.0 BIOSTATISTICS

14.1 Statistical Plan for Assessment

14.1.1 Implant Failure

The primary objective of this study is to assess for the reduction of implant failure associated with multi-beam IMRT, compared to our published historical implant failure rates associated with conventional radiation techniques. The primary endpoint is incidence of implant failure by the end of the study period (24 months post-IMRT for Group 1, and 30 months post-IMRT for Group 2).

Our published data and recent findings in the literature suggested that the implant failure rate (implants that are removed or replaced by another reconstruction) was 20% at 24 months post-IMRT for group 1 [20] and 30% at 30 months post-IMRT for group 2 [51]. Assuming that 1/3 of the patients we will enroll are going to be in group 1 and the remaining 2/3 will be in group 2, we set up the hypotheses that an implant failure rate of 26% or more is considered unacceptable while 16% or less is considered acceptable. Since the endpoint cannot be measured until 2 years after the treatment, we will utilize a one-stage design. We will test the hypothesis using a binomial test based on a cohort of 100 patients. We insist that at minimum 34 of them will be enrolled in group 1 and at minimum 66 will be in group 2, and we will combine them for the primary objective. We will claim that multi-beam IMRT significantly reduces the implant failure rate if no more than 20 patients have an implant failure after IMRT within 24 months of the treatment for patients in group 1 or within 30 months after IMRT in group 2. For this decision rule, we have a type I error (i.e., claiming multi-beam IMRT promising while it is not) rate less than 0.10 and a type II error (i.e., claiming multi-beam IMRT not promising while it actually is) rate less than 0.15.

Because there is no reason why local control or lung or other toxicities would be impacted secondary to treatment with multi-beam IMRT instead of conventional treatment, an early stopping rule in order to detect early recurrences was not deemed necessary.

We expect to accrue 3-4 patients per month. Thus, the trial should be completed within 3 years. Efforts will be made to follow-up every patient for at least 24 months (Group 1) or 30 months (Group 2). Since patients may drop off (for reasons unrelated to toxicity) or be lost to follow-up, we will enroll a total of 130 patients. However, only the first 100 patients (subject to the restriction that at minimum 34 are in group 1 and at minimum 66 are in group 2) who have been followed for at least 24/36 months from IMRT will be analyzed towards the primary objective. Only patients who are irradiated to a tissue expander or permanent implant will be counted in the analysis of the primary objective (i.e. patients in the cardiac substudies who do not receive IMRT to the tissue expander or implant will not be included in the analysis of the primary objective).

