1.0 PROTOCOL SUMMARY AND SCHEMA

[figure not shown]
Breast implant failure (defined as removal or replacement with another reconstruction) and capsular contracture are longstanding adverse effects of postmastectomy radiation (PMRT) in patients who have undergone immediate expander/implant reconstruction. These complications can impact cosmesis and quality of life. A prior departmental protocol, IRB #10-025, demonstrated the feasibility and safety of multi-beam IMRT in treating locally advanced breast cancer patients requiring comprehensive PMRT. By permitting the delivery of a more homogeneous radiation dose and fewer and smaller —hot spots— to the implant compared to conventional RT techniques, we hypothesize that multi-beam IMRT can minimize implant-related side effects of RT, leading to improved implant-specific outcomes and cosmesis in breast cancer patients with implant reconstruction undergoing PMRT. Efficacy is the primary endpoint of this study and is defined as relative 30% decrease in implant failure rates following the completion of IMRT. Secondary endpoints are to assess cosmesis, quantify minor revisional surgery rates and to evaluate the correlation between MRI changes in the implant and the degree of capsular contracture as ascertained by standard assessment methods. There are several exploratory endpoints in a subset of the study population: 1) to assess the feasibility of performing a cardiac PET scan in the IMRT treatment position in order to quantify the cardiac dose delivered to the heart 2) to assess early subclinical cardiotoxicity associated with IMRT, utilizing speckle tracking strain echocardiography, ultrasound of the brachial artery, cardiopulmonary exercise testing (CPET), fatigue and quality of life questionnaires and cardiac biomarkers 3) to assess the effect of IMRT on quality of life and fatigue.

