4.0 OVERVIEW OF STUDY DESIGN/INTERVENTION

4.1 Design

This is a Phase II trial examining the efficacy of multi-beam IMRT in reducing implant failure rates (primary endpoint), as well as the secondary endpoints of cosmesis, incidence of capsular contracture and minor revisional surgeries, and the correlation of MRI changes with clinical assessments of capsular contracture in breast cancer patients with implant reconstruction receiving PMRT. We will test the hypothesis that the 2-year probability of implant failure will be reduced by a relative 30% or greater compared to our aforementioned published experience of implant failure following PMRT with conventional radiation techniques.

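### Section 1.0 defines efficacy as a 30% relative decrease in implant failure, but the error rates in 14.1.1 are for a 38.5% decrease; at 30% the power is only 0.69 to 0.73

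*Combined protocol and SAP*

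**What the plan says.** Section 1.0 (Protocol Summary and Schema) states: "Efficacy is the primary endpoint of this study and is defined as relative 30% decrease in implant failure rates following the completion of IMRT". Section 4.1 (Design) puts the hypothesis slightly differently: "We will test the hypothesis that the 2-year probability of implant failure will be reduced by a relative 30% or greater". Neither section gives a power or a numerical baseline for the reduction.

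Section 14.1.1 (Implant Failure) gives the operating design. The historical failure rate "was 20% at 24 months post-IMRT for group 1 [20] and 30% at 30 months post-IMRT for group 2 [51". The assumed mix is that "1/3 of the patients we will enroll are going to be in group 1 and the remaining 2/3 will be in group 2". From these it sets the hypotheses: "an implant failure rate of 26% or more is considered unacceptable while 16% or less is considered acceptable". The test is a one-stage binomial test on 100 patients, with at least 34 in Group 1 and at least 66 in Group 2. The decision rule is: "We will claim that multi-beam IMRT significantly reduces the implant failure rate if no more than 20 patients have an implant failure after IMRT". For the false-positive risk of this rule the section says: "we have a type I error (i.e., claiming multi-beam IMRT promising while it is not) rate less than 0.10". For the opposite risk, missing a real benefit, its wording is: "a type II error (i.e., claiming multi-beam IMRT not promising while it actually is) rate less than 0.15".

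Section 14.1.1 thus shows where 26% comes from. It does not say where 16% comes from, and it does not mention the 30% target.

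**The concern.** The effect called efficacy in the summary is not the effect for which the error rates are given. Going from 26% to 16% is a larger reduction than 30%, so the stated type II error says nothing about a treatment that achieves exactly what 1.0 asks of it. Section 14.1.1 describes that error as calling IMRT not promising when it is. A reader who takes the meaning of promising from 1.0 will apply the 0.15 limit to a 30% reduction.

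Two misreadings follow. A negative result may be taken as good evidence against a 30% reduction when the trial had a sizeable chance of missing it. A positive result may be taken as showing a reduction of at least 30% when the test only compares the rate with the historical level.

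**Working it through.** **Inputs.** From 14.1.1: n = 100; success if 20 or fewer failures; null 26%; alternative 16%; historical rates 20% (Group 1) and 30% (Group 2); mix 1/3 to 2/3, or 34 to 66 by the enrolment minimums. From 1.0 and 4.1: a 30% relative reduction.

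**Formula.** With X the number of failures, the probability of declaring success at a true rate p is P(X ≤ 20) = Σ C(100, k) p^k (1 − p)^(100 − k), summed over k = 0 to 20. This is the type I error when p is the null rate. At a lower rate it is the power, and the type II error is one minus it.

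**Step 1: the plan's own figures.**
- Type II error at 16%: 1 − 0.8879 = 0.112. The stated limit of 0.15 is met.
- Null from the mix: (20 + 2 × 30)/3 = 26.67%, or (34 × 20 + 66 × 30)/100 = 26.6%. The plan uses 26%.
- Type I error at the stated 26%: 0.1027, just above the stated limit of 0.10.
- Type I error at the unrounded null: 0.0808 at 26.6% and 0.0786 at 26.67%. Treating the groups as separate binomials (34 patients at 20%, 66 at 30%) gives 0.0796. The limit is met for any null of about 26.07% or more.

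**Step 2: the effect that was designed for.** 1 − 16/26 = 38.5%. From the unrounded null it is 1 − 16/26.6 = 39.8%, or 1 − 16/26.67 = 40.0%.

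**Step 3: the same rule at a 30% reduction.**

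| Baseline | Rate after a 30% reduction | Power | Type II error |
|---|---|---|---|
| 26% | 0.26 × 0.7 = 18.2% | 0.730 | 0.270 |
| 26.6% | 0.266 × 0.7 = 18.62% | 0.693 | 0.307 |
| 26.67% | 0.2667 × 0.7 = 18.67% | 0.688 | 0.312 |
| 34 at 20%, 66 at 30% | 14% and 21% | 0.693 | 0.307 |

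**Step 4: what a success can look like.** Observed reduction from 26%:
- 18 failures: 1 − 18/26 = 31%
- 19 failures: 1 − 19/26 = 27%
- 20 failures: 1 − 20/26 = 23%

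The last two count as success but fall short of 30%. Measured from 26.6% they still do: 1 − 19/26.6 = 29% and 1 − 20/26.6 = 25%.

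**The case against.** The strongest reply is that nothing about power has been miscalculated. Section 14.1.1 names its own two rates, and its type II error is right for them. A design may be powered at an effect larger than the smallest one of interest. Section 4.1 asks for 30% or more, which 38.5% satisfies, and neither 1.0 nor 4.1 claims any power. The decision rule is explicit and decides the trial whatever percentage the summary gives. Section 14.1.1 claims only a significant reduction, not a demonstrated 30%.

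Most of this stands. A reader might infer that 4.1 contradicts 14.1.1; it does not, although no power is given at its 30% minimum. A reader might infer that the type II error is wrong, or that the sample size or cutoff is invalid; the documents support neither. What the reply leaves open is 1.0, which has no such allowance for larger effects, and the absence of any sentence linking 30% to 16%.

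A second reply is that 18.2% appears nowhere in the plan. That is true: it takes the 30% from one section and the 26% from another, and on the unrounded null the power is nearer 0.69 than 0.73. Hence the range. The only other historical rate given is 29% at 7 years (Section 3.0), and it does not reconcile the figures: 0.29 × 0.7 = 20.3%, where the power of the rule is 0.53.

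On type I error, a reader might infer an inflated false-positive rate. The excess is 0.0027 and arises only because the null was rounded down to 26%.

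**Conclusion.** The inconsistency is real and should be corrected, but it is one of definition and reporting and not a flaw in the test. The efficacy definition in 1.0 (30%) and the effect to which the error rates in 14.1.1 apply (38.5%) differ, and nothing reconciles them. At a true 30% reduction the rule misses the benefit 27% of the time from a 26% baseline, or about 31% from 26.6 to 26.67%. That is roughly twice the stated limit of 0.15. A positive result supports a failure rate below 26%; it does not establish a reduction of at least 30%. The stated type I limit fails narrowly at the stated null (0.1027) and holds at the unrounded one (0.079 to 0.081).

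These figures assume 100 evaluable patients, the cutoff of 20, exact binomial probabilities, and baselines taken from the group rates and mix in 14.1.1.

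**What to change.** Change wording only, and keep n = 100 and the cutoff of 20.

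- In 1.0 and 4.1, say that efficacy is judged by the 14.1.1 test against the historical 26% (success at 20 or fewer failures in 100), with 16% (a 38.5% relative reduction) as the design alternative. Add that a positive result shows a rate below 26%, not a reduction of at least 30%.
- In 14.1.1, give power as 0.89 at 16% and about 0.69 to 0.73 at a 30% relative reduction, depending on whether the 26.6 to 26.67% or the 26% null is used.
- In 14.1.1, restate the type I error as about 0.103 at 26% and about 0.08 at the unrounded 26.6 to 26.67%.

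Simply replacing 30% by 38.5% as the definition of efficacy would not do. Results of 17 to 20 failures would then be positive yet short of the definition (1 − 17/26 = 35% at best).

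The cost is that the stated operating characteristics look slightly less favourable. The change discloses the lower power at 30% and does not raise it. No data collection changes.

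### The printed null of 26% is slightly below the 26.6% that the protocol's own inputs give, and at 26% the exact type I error is 0.103, not below 0.10

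*Combined protocol and SAP*

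**What the plan says.** All of the relevant text is in Section 14.1.1 (Implant Failure) of the combined protocol and SAP. The historical failure rates are "20% at 24 months post-IMRT for group 1 [20] and 30% at 30 months post-IMRT for group 2 [51". The assumed mix is given as follows: "1/3 of the patients we will enroll are going to be in group 1 and the remaining 2/3 will be in group 2". From these the plan sets the hypotheses: "an implant failure rate of 26% or more is considered unacceptable while 16% or less is considered acceptable".

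The test is a one-stage design: "We will test the hypothesis using a binomial test based on a cohort of 100 patients". For that cohort the plan sets a floor for each group: "at minimum 34 of them will be enrolled in group 1 and at minimum 66 will be in group 2". Success is declared "if no more than 20 patients have an implant failure after IMRT", counted over each group's own follow-up period. The plan attaches two error limits to this rule. The first is quoted here: "type I error (i.e., claiming multi-beam IMRT promising while it is not) rate less than 0.10". The second puts the chance of missing a truly effective treatment (type II) below 0.15.

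The section does not say that 26% was rounded, truncated or set below the pooled rate on purpose. It also does not say how the two error rates were calculated.

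**The concern.** The assumption about the mix leads straight into the hypotheses, and its only visible use there is to combine the two group rates into one null. The combined value is not 26%, and rounding to a whole percent would give 27%.

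This figure is the null of the trial's primary test. An exact p-value or a stated error rate for the primary result will be calculated at it. If the printed null and the printed error rates do not belong together, a reader who checks one against the other finds a contradiction and cannot tell which of the two was intended.

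**Working it through.** **Inputs, all from Section 14.1.1.** Group rates 20% and 30%; mix 1/3 to 2/3; minimums of 34 and 66 in a cohort of 100; null 26%; alternative 16%; success if X ≤ 20, where X is the number of failures in 100 patients; type I error below 0.10; type II error below 0.15.

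**Step 1: the plan's own figures, at its printed rates.** By the exact binomial:
- Type I error = P(X ≤ 20 | n = 100, p = 0.26) = 0.1027. This is not below 0.10. Because the unacceptable region is 26% and above, the largest type I error over that region occurs at 26%, so 0.1027 is the figure that counts.
- Type II error = P(X ≥ 21 | n = 100, p = 0.16) = 0.1121. This is below 0.15, as stated.

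So the type II claim is reproduced and the type I claim is not.

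**Step 2: would another cutoff meet both limits at 26% against 16%?**

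| Success if X ≤ | Type I at 26% | Type II at 16% |
|---|---|---|
| 19 | 0.0658 | 0.1689 |
| 20 | 0.1027 | 0.1121 |
| 21 | 0.1521 | 0.0710 |

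No. A cutoff of 19 fails on type II; cutoffs of 20 and 21 fail on type I. Lower cutoffs only raise the type II error and higher ones only raise the type I error. The cause is the discreteness of the binomial count, not too few patients: with 92 patients and a cutoff of 18 both limits are met (0.096 and 0.142).

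**Step 3: the null that the inputs imply.**
- At 1/3 to 2/3: (1/3)(20%) + (2/3)(30%) = 26.67%.
- The minimums 34 and 66 sum to 100, so the mix in the analysed cohort is fixed: 34 × 20% + 66 × 30% = 6.8 + 19.8 = 26.6 expected failures per 100, or 26.6%.
- A pooled rate of exactly 26% needs 20w + 30(1 − w) = 26, so w = 0.40. A 40/60 mix is ruled out by the minimum of 66 in Group 2.

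**Step 4: type I error of the unchanged rule at the implied null.**

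| Null | P(X ≤ 20) | P(X ≤ 21) |
|---|---|---|
| 26% (printed) | 0.1027 | 0.1521 |
| 26.6% (34/66) | 0.0808 | 0.1228 |
| 26.67% (1/3 to 2/3) | 0.0787 | 0.1198 |
| 34 patients at 20% plus 66 at 30% (exact convolution) | 0.0796 | 0.1214 |

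At every version of the implied null the stated bound of 0.10 holds, and 20 remains the largest cutoff for which it does. The type II error is evaluated at 16%, so it stays at 0.1121. The bound first holds at a null of about 26.1%, only just above the printed value.

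**Step 5: where the stated bound may have come from.** At 26% the standard deviation of X is √(100 × 0.26 × 0.74) = 4.386. A normal approximation without continuity correction gives Φ((20 − 26)/4.386) = 0.086; with the correction, Φ((20.5 − 26)/4.386) = 0.105. A value below 0.10 could therefore come from an exact calculation at the unrounded null or from an uncorrected approximation at 26%. The text does not settle which.

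**The case against.** The best defence is that a null is a chosen threshold. The plan says the literature suggested 20% and 30% and then sets up hypotheses; it does not report 26% as a calculated mean, and the two inputs are themselves round figures. The unacceptable region is 26% and above, so it already contains 26.6% and 26.67%, and rejecting it also rejects the pooled historical rate. A lower null is harder to beat, so the shortfall does not favour IMRT. The decision is taken on a count, and that count stays at 20.

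All of this stands, and it rules out two stronger readings. A reader might infer that the primary benchmark is wrong and that the trial's conclusion would be measured against an invalid rate. The documents do not support that: the discrepancy is conservative and the go/no-go decision is identical under either null. A reader might also infer that the error rates were evaluated at a rate the inputs do not support. The documents do not show this either. The claimed type I bound agrees with 26.6% and not with an exact calculation at 26%, so the error rates may have been worked out at the unrounded null and only the printed percentage shortened.

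What the defence does not answer is the internal contradiction. Even if 26% was chosen on purpose, the type I statement attached to it is false under the binomial test that the plan names.

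**Conclusion.** The point holds as a minor inconsistency. The printed null is 0.6 to 0.7 percentage points below the value its inputs give. At the printed null the exact type I error is 0.1027, an excess of 0.0027 over the stated bound; at 26.6% it is 0.081 (0.080 with group-specific nulls) and the statement is true. Cutoff, sample size and type II error (0.112) are unaffected.

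This rests on two assumptions: that the binomial test is exact, and that the analysed cohort is exactly 34 and 66, as minimums summing to 100 require. Whether 26% is a truncation or a deliberate choice cannot be determined from the documents. The null and the type I statement are one issue and should be handled together, not counted as two.

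**What to change.** Either of two edits to Section 14.1.1 removes the contradiction.

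1. State the null as 26.6%, with its derivation (34 × 20% + 66 × 30% = 26.6 expected failures per 100). Keep the 20-failure rule, and quote the exact type I error as about 0.08 and the type II error at 16% as about 0.11. This makes the null, the rule and both error limits agree.
2. Keep 26%, say that it is a deliberately chosen threshold below the pooled historical rate, and correct the type I error to about 0.103.

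The first is the cleaner choice because it preserves the stated limits; the second keeps the stricter null. In both cases name the method (exact binomial).

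The cost is one sentence, with no change to sample size, cutoff or conduct. One side effect of the first option should be noted when editing: 16% is a relative reduction of 1 − 16/26 = 38% from the printed null and 1 − 16/26.6 = 40% from the restated one, so the distance from the 30% relative reduction named in Sections 1.0 and 4.1 grows slightly. That mismatch exists under either null and is a separate matter.

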For each patient, if even one out of the two planned studies are unable to generate doses for the heart segments, this patient will be considered as a —failure— towards the endpoint of feasibility. The approach will be declared feasible if we are able to obtain doses for all 17 segments of heart in at least 7 out of 10 patients. Should a patient drop out before they receive their follow-up scan, they will be replaced by another patient, unless the first scan was already a —failure—. We expect n=10 patients, but have budgeted enough scans for 12 patients, in the event a patient gets lost to follow-up/dies and cannot have the second scan, or declines the second scan. However, the decision rule is built by using the first 10 evaluable patients. This decision rule has the following probabilities of declaring success/feasibility.

True feasibility rate	0.85	0.80	0.70	0.60	0.50	0.45
Prob. of declaring feasible	95%	88%	65%	38%	17%	10%

We will further assess feasibility by correlating pre and post-IMRT measures of MBF/CFR with corresponding RT dose delivered to the ventricular myocardium on a global regional and segmental basis. The post-RT studies will help determine the incidence of MBF/CFR changes following radiation as determined by $^{13}\text{N-NH}_3$ PET imaging.

We will measure the correlation between the changes in flow and flow reserve and the dose level in 17 pairs (17 segments per PET data and 17 doses delivered by IMRT). Data will be visually examined first in order to choose the most appropriate correlation coefficient (e.g., Pearson or Spearman or Kendall's Tau, etc., though at this stage we expect that the nonparametric Spearman correlation coefficient will be used). Each patient will thus provide a correlation coefficient. The 10 correlation coefficients for 10 patients in the study will be summarized and descriptive statistics will be computed.

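### The primary decision rule has an exact type I error of 0.103, not below 0.10 as section 14.1.1 states; the figure should be restated

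*Combined protocol and SAP*

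**What the plan says.** Section 14.1.1 of the combined protocol and SAP gives every element of the primary decision rule.

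- Hypotheses: "an implant failure rate of 26% or more is considered unacceptable while 16% or less is considered acceptable".
- Test and number analysed: "We will test the hypothesis using a binomial test based on a cohort of 100 patients".
- Design: "we will utilize a one-stage design", so there is no interim look to allow for.
- Rule: "We will claim that multi-beam IMRT significantly reduces the implant failure rate if no more than 20 patients have an implant failure".
- False-positive rate claimed for this rule: "we have a type I error (i.e., claiming multi-beam IMRT promising while it is not) rate less than 0.10".
- False-negative rate claimed for the same rule: under 0.15.

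The 26% is introduced after two historical rates, 20% for group 1 and 30% for group 2, with an assumed one-third to two-thirds mix and minimum group sizes of 34 and 66. The section does not use the word exact and names no approximation.

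**The concern.** The null rate, sample size and cut-off together determine the type I error, so the claim can be checked without any outside assumption. A cut-off of 20 lies only 6 failures below the 26 expected under the null, where the standard deviation is √(100 × 0.26 × 0.74) = 4.39. That is about 1.37 standard deviations, close enough to a one-sided 0.10 boundary for the discreteness of the binomial to decide which side the rule falls on.

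At stake is the reported false-positive rate of the trial's only primary decision rule. The plan calls a result at or below the cut-off significant. If 20 failures are observed, a reader who recomputes the p-value will find it above the stated level, and the text would then have to be explained after the result is known.

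**Working it through.** **Inputs, all from section 14.1.1.** n = 100; p0 = 0.26; p1 = 0.16; success if X ≤ 20, where X is the number of failures.

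**Stated figures.** Type I = P(X ≤ 20 | 100, 0.26), given as below 0.10. Type II = P(X > 20 | 100, 0.16), given as below 0.15.

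**Exact binomial results, with the neighbouring cut-offs.**

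| Success if X ≤ | Type I at 26% | Type II at 16% | Meets both limits? |
|---|---|---|---|
| 19 | 0.0658 | 0.1689 | No (type II) |
| 20 | 0.1027 | 0.1121 | No (type I) |
| 21 | 0.1521 | 0.0710 | No (type I) |

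The type II figure is confirmed and the type I figure is not. Raising the cut-off increases type I and lowering it increases type II, so no cut-off at n = 100 meets both limits.

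**Would an approximation reproduce the claim?**

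- Normal, no continuity correction: z = (20 − 26)/4.387 = −1.368, giving type I 0.086. With standard deviation √(100 × 0.16 × 0.84) = 3.666, z = (20 − 16)/3.666 = 1.091, giving type II 0.138. Both limits are met.
- Normal, with continuity correction: z = (20.5 − 26)/4.387 = −1.254, giving type I 0.105; z = (20.5 − 16)/3.666 = 1.227, giving type II 0.110. Type I again exceeds 0.10.

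**How the plan computes its other decision rule.** Section 14.1.3 declares feasibility with at least 7 successes in 10 and tabulates the operating characteristics ("This decision rule has the following probabilities of declaring success/feasibility"). Comparing P(X ≥ 7 | 10, p) with the printed row:

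| True rate | 0.85 | 0.80 | 0.70 | 0.60 | 0.50 | 0.45 |
|---|---|---|---|---|---|---|
| Printed | 95% | 88% | 65% | 38% | 17% | 10% |
| Exact binomial | 0.950 | 0.879 | 0.650 | 0.382 | 0.172 | 0.102 |
| Normal, uncorrected | 0.908 | 0.785 | 0.500 | 0.259 | 0.103 | 0.056 |

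The printed row is the exact binomial.

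**Sensitivity to the null.**

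- Weighted historical rate at the planned sizes: (34 × 20% + 66 × 30%)/100 = 26.6%. At exactly one-third to two-thirds: 20%/3 + 2 × 30%/3 = 26.67%.
- Exact type I at a single rate of 26.6%: 0.081; at 26.67%: 0.079.
- Sum of Bin(34, 0.20) and Bin(66, 0.30): P(X ≤ 20) = 0.080.
- The same two-group sum with both rates multiplied by 26/26.6, so that the overall mean is 26%: 0.1014. Allowing for the two groups does not bring the figure below 0.10 at the printed null.
- The null at which P(X ≤ 20) equals 0.10 is about 26.07%.

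**Practical reach.** Only X = 20 is affected. Its probability is 0.037 at a true 26% and 0.057 at a true 16%.

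**The case against.** The best case for leaving the text alone has three parts.

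The size is trivial. An excess of 0.0027 over 0.10, in a single-arm phase II trial judged against round historical rates, would change nobody's conclusion, and the written count rule decides the outcome whatever the p-value. This stands as a statement about consequence. It does not make a strict inequality true.

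The protection is real on the plan's own inputs. If the cited rates of 20% and 30% hold in a 34/66 mix, the chance of a false claim is 0.080, and the bound fails only for nulls between 26% and about 26.07%. This also stands, and it is a reason to ask which benchmark was meant. But the printed hypothesis is 26%, and the error rate is stated for the rule built on it. If 26.6% was intended, the null is the figure that needs correcting.

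The section does not say exact, and an uncorrected normal approximation satisfies both bounds. That is a possible origin of the figure. It is not the natural reading of a binomial test, however, and the continuity-corrected version also exceeds 0.10. The feasibility table shows only how that smaller rule was computed. It supports the exact reading without proving it for the primary rule.

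**Conclusion.** The concern holds. With the printed null of 26%, 100 patients and a cut-off of 20, the exact type I error is 0.103, so the claim that it is below 0.10 is wrong as written. The type II claim is right, at 0.112. The discrepancy is small: 0.0027 in probability, affecting one possible outcome. The cut-off, sample size and conduct of the trial are untouched.

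The conclusion assumes that the binomial test is exact and that 26% is the intended null. Under the weighted historical rate of 26.6% to 26.7%, or under an uncorrected normal approximation, the stated bound would be met. The documents do not say that either was used.

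**What to change.** In section 14.1.1, keep the 26% null, the 100 patients and the cut-off of 20, and restate the exact error rates for that rule: type I about 0.103 at 26% and type II about 0.11 at 16%. Say that both come from the exact binomial distribution.

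The sponsor should also confirm whether 26% or the weighted 26.6% was the intended benchmark. Only if it was 26.6% should the null be restated instead. The existing type I bound is then true (about 0.08), and the type II figure does not move because it depends only on the 16%.

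The cost is one sentence. Making the change before the failure count is known avoids any appearance of adjusting the error level to the result.
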